- Patient of legal age but subject to legal protection measure or unable to express their consent
- Patient suffering from uncontrolled epilepsy
- Patient with visual or auditory disorders
- Patient suffering from claustrophobia or motion sickness
- Patient with face infection
- Patient with dissociative psychiatric pathologies and autism

After consulting the patients' medical records, and checking that there are no exclusion criteria, the investigators will introduce themselves to the patients and their families, informing them that they are eligible and offering them to take part in the study.

[figure not shown]
Patients will be informed that the study aims to investigate the immersive effect of VR during intravenous cannulation procedure, and they will be provided with a patient information sheet and flyer.

If the patient agrees in principle to take part in the study, and after obtaining informed, signed, written consent, each patient will be given a personalized schedule of the various management appointments and the questionnaires used as part of the protocol.

Interventions:

Patients will benefit from the standard of care for their first visit, then they will have a VR session on their second visit, then another session in VR for their third visit. The VR session starts 5 minutes before the intravenous cannulation procedure, 10 minutes during the procedure and 5 minutes after, for a total of 20 minutes. Before and after the intravenous cannulation procedure, the investigator will complete the Case Report Form for data collection from patients.

All participants will complete questionnaires before and after the procedure at visit 1 (V1), V2 and V3. The interval between visits is 3 weeks, in line with clinical practice at the referral centre.

The two options for managing anxiety and general symptoms are:

1) Standards of care (SOC) :

Thalassemia patients require lifelong monthly blood transfusions to survive. During routine visits, an experienced healthcare provider inserts intravenous cannulation under aseptic technique. Children are escorted by parents to offer support and distraction. This short procedure is accompanied by pain and anxiety for all the involved parties.

2) Virtual reality (VR)

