HEALTHY MIND© VR (Paris, France): a 15-minute VR therapeutic session immersing the patient in an artificial world created from computer-generated images using software connected to the PICO 4E headset. The patient can choose one of several types of environments (beach, mountains, lake and others) using synthetic animated images, breathing exercises and advanced psychological/relaxation principles such as cardiac coherence or hypnotic verbal accompaniment.

Variables will be reported in a standardized way in the CRF in the following order:

- Before intravenous cannulation
 - Patient identification number
 - Patient demographics (gender and age)
 - Inclusion and exclusion criteria
 - Patient's VAS for pain intensity
 - Patient's VAS for anxiety
 - Patient's VAS for fatigue
 - Patient's VAS for cramps and heart rate measurement
- After intravenous cannulation:
 - Characteristics of intravenous cannulation. Specificity.
 - Patient's VAS for pain intensity
 - Patient's VAS for anxiety
 - Patient's VAS for fatigue
 - Patient's VAS for cramps and heart rate measurement
 - Patient's VAS for comfort and acceptability of VR headset use

Data collection

	Pre inclusion V0 (*)	Visite 1		Visite 2		Visite 3	
		Before	Post	Before	Post	Before	Post
Screenning and information	✓						
Consent form signed	✓						
Demographic Data ¹		✓					
Physiological data ²		✓	✓	✓	✓	✓	✓
VAS ³ Anxiety, Pain and Fatigue		✓	✓	✓	✓	✓	✓
HAD scale		✓			✓		✓
Patient/Family Satisfaction			✓		✓		
Professional Satisfaction							✓

Expected Outcomes

Primary outcomes: Evaluated by the Visual Analogue Scale (VAS)

- Evaluate the impact of VR-induced 3D immersion on anxiety during cannulations through visualization of Healthy Mind VR therapeutic sessions (using a PICO 4E VR headset). Comparison of patients' anxiety levels before and after the procedure with and without VR. Assessed by visual analog scale (VAS).
- Evaluate the impact of VR-induced 3D immersion pain during cannulations through visualization of Healthy Mind VR therapeutic sessions (using a PICO 4E VR headset). Comparison of patients' pain levels before and after the procedure with and without VR.

Secondary outcomes: Evaluated by the Visual Analogue Scale (VAS)

- Evaluation of fatigue levels after the procedure for patients with and without VR.

- Examine factors associated with boredom and weariness with and without VR.
- Evaluation of patient satisfaction with and without VR.

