- Assessment of healthcare professionals' satisfaction levels during and after the procedure with and without VR.
- Assessment of family members' satisfaction levels during and after the procedure with and without VR.
- Assessment of other outcomes of interest (exploratory)
 - Evaluation of the heart rate with and without VR (cardiac frequency)

Sample size calculation:

Due to the exploratory nature of the study, the sample size was calculated on the basis of the number of possible orders of relaxation sessions, which was calculated as follows: 3 types of options x 3 x 2 = 18 possible session orders.

At least two different patients had to be enrolled for each type of option (i.e. 36 patients), to ensure a homogeneous distribution of the different possible orders of relaxation within the study population. 100 patients had to be enrolled in the study, to take account of patients lost to follow-up and missing data. Study power was set at 80% to demonstrate a clinically significant difference greater than 2, with an alpha threshold of 0.05.

Statistical analysis of primary objectives:

The difference between two sessions (VR vs SOC) will be followed by a comparison of the proportions of patients who achieved at least a 25% improvement in anxiety, pain, fatigue, and depression, assessed by the VAS and HAD scale in post-cannulation procedure. The value provided to patients in the VR session during intravenous cannulation procedure and patients with SOC, will be compared using Student's t-test, after verification of the homoscedasticity hypothesis by a Levene's test.

If this hypothesis is not verified, the Mann-Whitney test will be performed, for which the number of patients required to maintain 90% power is 35 per group. If the reduction is not 25% but only 20%, with a power of 80%, this difference will be highlighted.

A 2-factor repeated-measures ANOVA model (VR vs. non-VR session and time before vs. time after) will be developed. Another statistical model will be developed, in order to see the time and session effect and to see if there is an interaction between the 2 factors. Finally, the correlation between basal anxiety scores on the different VAS, HAD scales will be estimated using Pearson's or Spearman's coefficients; the same statistical approach will be used to assess correlations between basal anxiety and their levels measured after the cycles by the VAS.

Statistical analysis of secondary objectives:

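### The primary analysis uses independent-group tests on paired sessions and an undefined 25% improvement criterion, and states no deciding analysis or pain/anxiety success rule

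*Combined protocol and SAP*

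**What the plan says.** **Tests.** Statistical analysis of primary objectives opens with "The difference between two sessions (VR vs SOC) will be followed by a comparison" of responder proportions, namely a "comparison of the proportions of patients who achieved at least a 25% improvement in anxiety, pain, fatigue, and depression". For the instruments and the time point, it says that these are "assessed by the VAS and HAD scale in post-cannulation procedure". Session values are then compared by Student's t-test after Levene's test. Failing that, "the Mann-Whitney test will be performed, for which the number of patients required to maintain 90% power is 35 per group". Next, "A 2-factor repeated-measures ANOVA model (VR vs. non-VR session and time before vs. time after) will be developed", followed by a further model that is not specified. Under Interventions, all patients have SOC at visit 1 (V1) and VR at V2 and V3.

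**Outcomes.** Expected Outcomes makes VAS anxiety and VAS pain primary, each as a contrast of levels before and after the procedure under both conditions. Study Objectives says the same. Fatigue is secondary, and depression is not a listed outcome. Sample size calculation gives 80% power for a difference above 2 at alpha 0.05 and calls the study exploratory. Study Aim expects a conclusion on effectiveness.

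**Timing.** Interventions states: "All participants will complete questionnaires before and after the procedure at visit 1 (V1), V2 and V3". The Data collection table has VAS anxiety, pain and fatigue before and post at all three visits. HAD is at V1 Before, V2 Post and V3 Post. The row "Patient/Family Satisfaction" is at V1 Post and V2 Post. The list headed "Variables will be reported in a standardized way in the CRF in the following order" has no HAD item. Statistical analysis of secondary objectives applies the 25% rule to satisfaction as well.

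**The concern.** A 25% improvement needs a starting value, and none is stated. Different starting values give different responders from the same data, and any of them can disagree with the difference in mean score. Several analyses sit under the primary objectives and none is named as deciding, so the choice could be made after the results are seen. The named score tests assume two separate groups of patients, but this design has one group measured repeatedly. Pain and anxiety share one alpha with no rule for combining them. For depression, the analysis asks for a measurement that the schedule does not contain.

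**Working it through.** **1. The plan's own figure.** The 35 per group at 90% power has no stated SD. With the plan's difference of 2 and an assumed SD of 2.5, n = 2(1.960 + 1.282)² × 2.5² / 2² = 32.8, so 33. Dividing by the Mann-Whitney efficiency 3/π = 0.955 gives 34.6, so 35. The figure therefore reproduces only with an assumed SD, and as two independent groups. The plan adds that a 20% reduction would be shown with 80% power. Scaling the effect by 20/25 = 0.8 at the same n gives Φ(0.8 × 3.242 − 1.960) = Φ(0.633) = 73.7%. As a 25-point difference in responder proportions, 90% power would need 57 to 82 per group for assumed SOC rates of 10% to 50%. So 35 was not sized for that comparison over this range.

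**2. Independent tests on paired data.** With equal SD σ and within-patient correlation ρ, the mean difference has variance 2σ²(1 − ρ)/n, but the independent-group test uses 2σ²/n. Its true two-sided error is 2[1 − Φ(1.96/√(1 − ρ))].
- ρ = 0.5: 1.96/0.707 = 2.77, error 0.56%.
- ρ = 0.3: 1.96/0.837 = 2.34, error 1.9%.

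The correlations are assumptions.

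**3. Three possible references for 25%.**
- *Same-visit pre-score.* Gives a proportion for each session. For pain, the starting score precedes the needle. A percentage fall from 0 is undefined and no rule is given. With pre-score 1, the responder threshold is 0.75. Needle pain of 6 under SOC and 2 under VR both exceed it, so a 4-point benefit counts as non-response twice.
- *V1 Before.* Also gives an SOC and a VR proportion for VAS. The same problem arises for pain.
- *SOC post score.* Each patient has one status, so there is no SOC proportion to compare.

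Size of the same-visit problem, by simulation. Assumptions: integer 0–10 scores, post-needle means 5 (SOC) and 3 (VR), SD 2.2, between-session correlation 0.5, non-zero pre-scores with SD 1.5, no correlation between pre and post scores. Among patients whose needle pain falls by at least 2 points, 67%, 55%, 42% and 25% are non-responders in both sessions at pre-score centres 1.5, 2.5, 3.5 and 5. With a pre/post correlation of 0.7 these become about 77%, 64%, 44% and 20%.

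SOC-post reference with **no** VR effect (SD 2.2, correlation 0.5, SOC scores of 0 excluded):

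| Assumed SOC mean | ≥25% better | ≥25% worse |
|---|---|---|
| 5 | 29% | 32% |
| 3 | 40% | 33% |
| 2 | 46% | 31% |

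At low SOC scores a benefit appears where none exists. At mean 2, 25% of SOC scores are 0.

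**4. Timing, side by side.** VAS: all six time points, so data exist for any reference. HAD: no value after SOC and none before either VR session. A post-cannulation VR versus SOC comparison of depression therefore has no SOC value, and no visit gives a within-visit change. Satisfaction: one SOC and one VR value, so a paired comparison exists but no within-visit percentage change.

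**5. Success rule.** If a win on either outcome suffices and each is tested at 0.05, family-wise error is 1 − 0.95² = 9.75% if independent, 9.1% at correlation 0.5 and 7.8% at 0.8. If both are required there is no inflation. Joint power is then 0.8² = 64% if independent, or 69% at correlation 0.5, when each test has 80%.

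**The case against.** The strongest reply is that the plan says more than it seems to. Study Objectives, Expected Outcomes and the session-by-time ANOVA all contrast before with after, which points to within-visit change. The section's word order and the power statement suggest that the score difference leads. The ANOVA can handle the pairing. The study calls itself exploratory. All of this stands as indication, but none of it defines the 25% criterion, names a deciding test or removes the independent-group tests. The exploratory label also sits beside a stated intention to conclude on effectiveness.

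Several stronger readings are tempting and not supported:
- *The responder analysis lacks its data.* For VAS it does not. The certain misfit is HAD.
- *Satisfaction cannot be compared.* V1 Post and V2 Post form a pair.
- *The t-test produces false positives.* With positive within-patient correlation it errs the other way.
- *Error is inflated to 9.75%.* Only if either outcome suffices, which the plan does not say.
- *The 25% rule destroys power.* Under the working assumptions with pre-scores centred on 2.5, exact McNemar power is 99% with no zero pre-scores. With 25% zeros it is 89–96% if zeros are dropped. It falls to 41–78% only when half are zero.
- *Interventions flatly contradicts the table.* Questionnaires may be meant generically, and VAS satisfies the sentence. The table's footnotes are not in the available text. Clarification is the right request.

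**Conclusion.** The point holds as a should-fix matter. Three parts rest on the text alone: independent-group tests are planned for paired sessions; no HAD is tabulated after SOC although a post-cannulation depression comparison is planned; and the 25% reference, the deciding analysis, the VR value and the either/both rule are not stated. A percentage fall in pain from a pre-needle score of 0 is undefined whatever the distribution. The sizes are illustrative, because the documents give no score distributions or correlations. The HAD conclusion depends on the table as reproduced being correct. The score data can still answer the main question, so this is a defect of specification and not a fatal one.

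**What to change.** - For pain and for anxiety, name one deciding analysis: the within-patient VR minus SOC difference with 95% CI, by a paired test or mixed model. Fix in advance whether VR means V2, V3 or their average.
- State openly whether it uses the post-cannulation score or the session-by-time interaction of the planned ANOVA, and make the other supportive. The post score is preferable for pain because the pre-score precedes the needle, but it departs from the before/after wording of the objectives and outcomes.
- Replace Student and Mann-Whitney with paired versions.
- State whether either outcome suffices (then Holm at 0.05) or both are required (no split).
- Keep the 25% proportion as description only, with its reference and zero rule stated and no inference drawn from it.
- Clarify HAD and satisfaction timing across Interventions, the CRF list and the table. If the table stands, report HAD descriptively as change from V1 Before and compare satisfaction as paired V2 versus V1.
- Move fatigue to the secondary analysis and depression to exploratory.

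**Cost.** Wording only, with no new data if the table stands. With Holm, the detectable effect at 80% power is approximately (z for 1 − α/2 + 0.842)/√n. For 100 complete pairs this is 2.802/10 = 0.28 SD of the paired difference, rising at worst to 3.083/10 = 0.31 (exact t: 0.283 and 0.312). The plan's 100 allows for losses around a core of 36. At 36 pairs the exact values are 0.48 and 0.53 SD. Requiring both outcomes instead costs the joint power shown in step 5. None of this removes the fixed visit order.

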We propose to conduct an interventional cross-over study with a cohort of around 100 patients, where initial data is collected without VR for measuring baseline, then VR is implemented twice in a 3-week interval between sessions. We will investigate the impact of VR software on patients' pain and anxiety during the intravenous cannulation procedure, compared with a standard care program. Our primary outcomes involve assessing patient pain and anxiety, while secondary outcomes are fatigue, boredom, and overall patient satisfaction.

Pain and anxiety will be measured both subjectively (VAS) and objectively (cardiac frequency) as secondary exploratory measures. We will also look to assess healthcare providers' and family members' satisfaction levels pre and post VR intervention. The aim of this study is to evaluate the benefits of VR programs in reducing patients' pain and anxiety.

Introduction

Background and Rationale:

Hemoglobinopathies, specifically β -thalassemia, are a significant health concern in the UAE, affecting 8.5% of the population [1,2]. These genetic disorders often require frequent blood draws, chelation therapy, and transfusions, causing stress and impacting quality of life for patients [3].

Repeated pain in children with chronic diseases such as thalassemia can cause behavioural changes in their adolescence, such as anxiety, social problems, and decreased attention. This condition can further impact the quality of life of thalassaemic children as adults [4]. Therefore, nurses must provide specific interventions to improve the child's comfort during invasive procedures.

Virtual reality (VR) is a technology that enables patients to be projected, via a computer system, into an immersive 3-dimensional virtual world. This specificity gives VR a highly immersive and distracting capacity. VR effectively diverts the patient's attention away from the source of pain, thereby diminishing his or her conscious perception of it [5,6].

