The difference between two sessions (VR vs SOC) will be followed by a comparison of the proportions of patients who achieved at least a 25% improvement in satisfaction, assessed by the VAS. Comparison will be carried out using the same method used for primary objectives.

Risk factors associated with dissatisfaction will be explored using uni and multivariate logistic regression models.

Overall ethical considerations

This study is useful both for its scientific contribution and for improving the comfort of thalassemia patients undergoing invasive procedures such as intravenous cannulation. Through this study, we will gain insight into the impact of virtual reality as an adjuvant to care for intravenous cannulations.

Our research will be conducted in accordance with the Declaration of Helsinki and the National Act on Research Involving Human Subjects. We will ensure that no coercion or pressure to participate is exerted on patient-participants. Written informed consent will be obtained from each participant. At any time and without explanation, participants may leave the study without any effect on future care, treatment or working conditions.

With the exception of necessary personal data (socio-demographic information), members of the research team will maintain confidentiality with patient information. Participant data will be anonymised or coded as appropriate and stored securely.

Limitations

A limitation of our study is that randomising the order of intervention sessions was not favourable for our investigation. Because our participants all suffer from chronic disease, the most appropriate way to get a baseline for pain and anxiety perception is before exposure to VR intervention. If done in an alternative manner, i.e. starting with a VR session and then not having VR, it would be more likely for patients to over-report their feelings of pain or anxiety, thus skewing the results. Hence, ordering the sessions in the way that was ultimately decided was, we believe, in favour of reducing bias.

The results of this study will be applicable to all population groups which do not fall under our exclusion criteria (as mentioned in the methods).

Project Timeline

	Feb 2024	Mar 2024	15th April – 15th June	July 2024	Aug 2024	Nov-Dec 2024
IRB Submission						
Site preparation, staff training						
Screening and inclusion						
Data management						
Statistical analysis						
Dissertation writing						

Acknowledgements

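### The primary-objectives analysis includes fatigue (a declared secondary outcome) and depression (on no outcome list), and no rule stops either being reported as a primary finding

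*Combined protocol and SAP*

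**What the plan says.** The summary at the start of the document is explicit: "Our primary outcomes involve assessing patient pain and anxiety, while secondary outcomes are fatigue, boredom, and overall patient satisfaction". *Expected Outcomes* agrees. Its primary list, which names the VAS as the instrument, has two entries: anxiety, and pain ("Comparison of patients' pain levels before and after the procedure with and without VR"). Fatigue heads the secondary list: "Evaluation of fatigue levels after the procedure for patients with and without VR". The aim, objectives and hypothesis also speak only of pain and anxiety.

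*Statistical analysis of primary objectives* then defines the VR-versus-SOC responder comparison as a "25% improvement in anxiety, pain, fatigue, and depression, assessed by the VAS and HAD scale in post-cannulation procedure". That is four constructs on two instruments. In the supplied text this is the only mention of depression. The HAD scale is in the *Data collection* table but is tied to no listed outcome.

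*Statistical analysis of secondary objectives* plans a comparison of the proportion with at least a "25% improvement in satisfaction, assessed by the VAS", using the primary-objective methods, and regression models for dissatisfaction. It does not mention fatigue.

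The only error-rate statement is in *Sample size calculation*: "Study power was set at 80% to demonstrate a clinically significant difference greater than 2, with an alpha threshold of 0.05". It names no endpoint, and no section says what counts as success or how several endpoints share that alpha.

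**The concern.** The outcome lists and the analysis section disagree about which endpoints are primary. An analyst who follows the analysis section would report fatigue and depression alongside pain and anxiety, under the primary heading. A reader of the outcome lists would expect fatigue among the secondary results and no depression result at all.

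The trial's question is whether VR reduces pain and anxiety at cannulation. If both VAS results were null and fatigue happened to reach 0.05, nothing in the plan would stop that being presented as a finding on the primary objectives. For fatigue this is a practical possibility, because its VAS is scheduled before and after the procedure at all three visits. Each added endpoint also raises the chance of a false primary claim.

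**Working it through.** **Placement of each endpoint**

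| Endpoint | Outcome lists | Analysis section | Measured after SOC (visit 1)? |
|---|---|---|---|
| Anxiety, VAS | Primary | Primary | Yes |
| Pain, VAS | Primary | Primary | Yes |
| Fatigue, VAS | Secondary | Primary only | Yes |
| Depression, HAD | Not listed | Primary only | Not in the table as extracted |

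The last column comes from the *Data collection* table, which shows HAD before the procedure at visit 1 and after it at visits 2 and 3. *Interventions* says instead that questionnaires are completed before and after the procedure at every visit. On the table, a post-procedure HAD comparison of VR with SOC cannot be made. On the text, it can. The table may have been damaged in extraction, so both cases are carried forward.

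**Chance of at least one false-positive primary result**

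The plan gives no figure of its own to reproduce, only alpha = 0.05. Assume one test per endpoint, each with a true 5% false-positive rate, independence, and no effect on any endpoint. With *k* endpoints the chance is 1 − 0.95^*k*:

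- Two declared outcomes: 1 − 0.95² = 0.0975, or 9.8%.
- Fatigue added: 1 − 0.95³ = 0.1426, or 14.3%.
- Fatigue and HAD depression added: 1 − 0.95⁴ = 0.1855, or 18.5%.

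**Part due to the mismatch itself**

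This is the chance that pain and anxiety are both null while an added endpoint is falsely positive:

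- Fatigue only: 0.95² × 0.05 = 0.9025 × 0.05 = 0.0451, or 4.5%.
- Fatigue or depression: 0.95² × (1 − 0.95²) = 0.9025 × 0.0975 = 0.0880, or 8.8%.

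**Effect of correlation**

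The documents give no correlations, so a common correlation ρ was assumed and normal test statistics were simulated (one million draws per case, two-sided 0.05):

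| Assumed ρ | Two endpoints | Four endpoints | False positive only from fatigue or depression |
|---|---|---|---|
| 0.3 | 9.5% | 17.4% | 7.9% |
| 0.5 | 9.1% | 15.6% | 6.5% |
| 0.7 | 8.3% | 13.1% | 4.7% |

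**After realignment**

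With only pain VAS and anxiety VAS in the primary family, each at 0.05 and either one sufficing, 9.8% remains under independence. Testing each at 0.025 gives 1 − 0.975² = 0.0494, within 5%. If both must succeed, no split is needed.

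**The case against.** **The study is exploratory.** *Sample size calculation* says so, and this reduces the confirmatory weight of any single test. But the same section sets 80% power and alpha 0.05, and *Study Aim* expects a conclusion on effectiveness. The label does not reconcile an outcome list with an analysis that contradicts it.

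**No success rule is stated.** A reader might infer that the plan would declare the trial positive on any one of four endpoints. The documents do not say that. The summary, aim, hypothesis and outcome list all point to pain and anxiety, and a section heading does not redesignate endpoints. What stands is narrower: nothing rules out reporting a fatigue or HAD result as primary.

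**For fatigue the issue is mostly one of label.** This is fair. Secondary comparisons use the same methods, so moving fatigue would not change its test. The label still decides what may be claimed from the result.

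**The error rates can be overstated.** A reader might count anxiety on both VAS and HAD, giving five tests and 1 − 0.95⁵ = 22.6%. That figure, like 18.5%, needs HAD scores after the SOC procedure, which the extracted schedule does not show. On that schedule fatigue is the only addition and 14.3% is the relevant figure. More than half of even the 18.5% (9.75 points) is already there with the two declared outcomes. The 5% per test is itself an idealisation: the planned t-test or Mann-Whitney test is for independent groups although the same patients are measured repeatedly, and visit order is fixed. The ANOVA and the further model would add tests.

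**Depression might be called no outcome at all.** That goes too far. It is on no outcome list, but an analysis is planned and the instrument is scheduled.

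**Conclusion.** The inconsistency is real. It lies in intact prose under clear headings, and it does not depend on the sample size or on how the schedule is read. Fatigue is declared secondary but analysed only under the primary heading. Depression is analysed there without being a listed outcome.

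On the idealised assumptions above, adding fatigue raises the chance of a false primary finding from 9.8% to 14.3%. It reaches 18.5% only if HAD depression can also be compared after SOC. At assumed correlations of 0.3 to 0.7, the four-endpoint figure falls to between 17.4% and 13.1%, against 9.5% to 8.3% for two. These figures illustrate scale and do not predict this trial's actual error rate.

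The point affects what may be claimed as primary. It does not invalidate the pain and anxiety comparisons, and it should be settled before the data are analysed.

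**What to change.** - In *Statistical analysis of primary objectives*, restrict the VR-versus-SOC comparison to pain VAS and anxiety VAS. State whether both must succeed (each at 0.05) or either suffices (0.025 each).
- Move fatigue VAS to *Statistical analysis of secondary objectives*.
- Label HAD depression and HAD anxiety as secondary or exploratory, or remove them from the VR-versus-SOC comparison. The first option keeps the post-VR HAD data already scheduled; cutting HAD back to a baseline descriptor would discard them for no need. The planned correlation analysis can stay either way.
- Reconcile the HAD row of the *Data collection* table with the statement in *Interventions* that questionnaires are completed before and after the procedure at every visit.

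The cost is rewording of the two analysis sections and one scheduling clarification. The realignment needs no new data. The small downside is that fatigue and HAD results can no longer be presented as primary. If the either-one rule is chosen, each primary test also faces the stricter 0.025 threshold.

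### The planned VR-versus-standard-care comparison on the HAD scale, including depression, has no scheduled standard-care value after cannulation

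*Combined protocol and SAP*

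**What the plan says.** All references are to the combined protocol and SAP.

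- **Statistical analysis of primary objectives.** VR and SOC sessions are compared on the proportion of patients with "at least a 25% improvement in anxiety, pain, fatigue, and depression", "assessed by the VAS and HAD scale in post-cannulation procedure". Values are then compared by Student's t-test, or by Mann-Whitney if the variances differ. The same section plans to correlate baseline anxiety across the VAS and HAD scales, and baseline anxiety with later VAS levels.
- **Interventions.** The order is fixed: "Patients will benefit from the standard of care for their first visit, then they will have a VR session on their second visit". The third visit is also VR. The section adds: "All participants will complete questionnaires before and after the procedure at visit 1 (V1), V2 and V3". It does not say which questionnaires.
- **Data collection (schedule table).** HAD is ticked at V1 Before, V2 Post and V3 Post. VAS anxiety, pain and fatigue are ticked before and after at all three visits. The row "Professional Satisfaction" is ticked once, at V3 Post.
- **Case report form list.** The variables listed before and after cannulation do not include HAD.
- **Opening summary and Limitations.** The first visit is described as a baseline: "initial data is collected without VR for measuring baseline", and "the most appropriate way to get a baseline for pain and anxiety perception is before exposure to VR intervention". Neither passage mentions HAD.
- **Secondary outcomes.** Healthcare professionals' satisfaction is to be assessed under both conditions. The opening summary speaks of provider satisfaction before and after VR.

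**The concern.** A proportion improved under SOC needs a HAD value taken after cannulation in the SOC session. None is scheduled. If the site follows the table, the analyst must either drop a comparison that is written under the primary objectives, or set a SOC value taken before the needle against a VR value taken after it and call the result VR versus SOC.

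The gap cannot be repaired afterwards, because V1 is the only SOC visit. Nor can the site settle it from the text. The general sentence in Interventions might include HAD, the table says otherwise, and the case report form list is silent.

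**Working it through.** No sample size or power figure is involved. The check sets the schedule against what the stated comparison needs.

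**Step 1: condition at each visit (Interventions).** V1 = SOC; V2 and V3 = VR. Visits are 3 weeks apart, so V3 is 3 + 3 = 6 weeks after V1.

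**Step 2: schedule rows (Data collection).** After the pre-inclusion column there are six time points.

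| Row | V1 Before (SOC) | V1 Post (SOC) | V2 Before (VR) | V2 Post (VR) | V3 Before (VR) | V3 Post (VR) |
|---|---|---|---|---|---|---|
| VAS anxiety, pain, fatigue | yes | yes | yes | yes | yes | yes |
| HAD | yes | – | – | yes | – | yes |
| Patient/family satisfaction | – | yes | – | yes | – | – |
| Professional satisfaction | – | – | – | – | – | yes |

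HAD counts per patient:
- time points covered: 3 of 6
- SOC Post: 0 of 1
- VR Post: 2 of 2
- visits with a before/after pair: 0 of 3

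**Step 3: what the comparison needs.** The SOC proportion is the share of patients for whom (starting score − SOC Post score) / starting score ≥ 0.25. The SOC Post score does not exist for HAD, so this proportion cannot be formed. The VAS row covers anxiety, pain and fatigue but not depression, so depression has no substitute instrument.

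**Step 4: what the scheduled data can give.** Let v be the VR effect, w the before/after change within a visit, and t3 and t6 the changes over 3 and 6 weeks, in a simple additive description.

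- V2 Post − V1 Before = v + w + t3
- V3 Post − V1 Before = v + w + t6

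Every scheduled non-VR HAD value is a Before value and every scheduled VR value is a Post value, so v and w cannot be separated.

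**Step 5: what one extra form would give.** With HAD at V1 Post, V1 Post − V1 Before = w. Then V2 Post − V1 Post = (v + w + t3) − w = v + t3. The before/after part drops out and the period part stays.

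**Step 6: text against table.** If the general sentence in Interventions includes HAD, it conflicts with the schedule in three cells: V1 Post, V2 Before and V3 Before. If it does not, the table stands and Step 3 applies.

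**Step 7: reading of the table.** The table was extracted from PDF, so column position matters. The HAD row has the same seven columns as the fully ticked VAS row. Under any alignment, three ticks cannot supply before and after values at three visits.

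**The case against.** The best defence is that the HAD row was designed on purpose. The document treats the first visit as a baseline, and the planned correlation of baseline anxiety across VAS and HAD gives the V1 Before HAD score a stated use. On that view the fault is one loosely worded analysis sentence, not a forgotten measurement. This stands as an explanation of the row, and it is why deleting or relabelling is the default fix. It does not rescue the sentence, because change from a pre-VR baseline is not a post-cannulation comparison of VR with SOC.

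It is also fair to say that HAD may hardly move within a visit, so that w is near zero. The documents give no HAD values to show this either way, and without V1 Post it cannot be checked.

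Three stronger readings are tempting and are not supported:

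- **That the primary outcomes are compromised.** They are not, on this point. Primary and secondary outcomes are headed as VAS-assessed, and VAS anxiety and pain are scheduled at all six time points. Depression is not a listed outcome, and HAD anxiety is supplementary.
- **That a planned ANOVA fails on HAD.** The plan says "A 2-factor repeated-measures ANOVA model (VR vs. non-VR session and time before vs. time after) will be developed" but does not assign that model to HAD, so no stated ANOVA fails.
- **That staff satisfaction without VR will certainly not be obtained.** The V3 form might ask about both conditions. The form and the table's footnotes are not visible in the copy reviewed, and no test of staff satisfaction is specified.

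**Conclusion.** The concern holds for HAD. The VR-versus-SOC comparison of at least 25% improvement on HAD after cannulation, for depression and for anxiety, cannot be run on the scheduled data, because SOC Post is 0 of 1. This rests on V1 being the only SOC visit, on the schedule table governing over the general sentence in Interventions, and on the column reading in Step 7.

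The size of any bias from using V1 Before in its place cannot be computed, because no HAD values are given. The inconsistency should be corrected, but no conclusion on the primary VAS outcomes depends on it. The finding concerns which data are collected; it passes no judgement on the fixed SOC-then-VR order.

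The professional-satisfaction point is minor: the text promises an assessment under both conditions, and the schedule shows one tick at a VR visit. This is a mismatch to reconcile, not a failed analysis.

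**What to change.** 1. **Reconcile the text and the table.** State in Interventions which questionnaires are taken at which time points, so that HAD agrees with the schedule. No cost.
2. **Default.** Remove HAD and depression from the VR-versus-SOC responder comparison, or relabel it: *descriptive change from pre-VR baseline (V1 Before) to V2 Post and V3 Post; not a VR-versus-SOC comparison*. This needs no new data and remains possible after collection has ended.
3. **Alternative, only if V1 visits are still to come.** Add HAD at V1 Post. Compare V2 Post with V1 Post within patient, separately for the HAD anxiety and depression subscales, with V3 Post as supportive. State that this paired analysis replaces the two-sample tests for HAD and that the period effect remains. The cost is one form per patient at an existing visit: 3 to 4 forms each, or about 300 to 400 in total for 100 patients.
4. **Minor.** For professionals' satisfaction, add a rating at V1 Post, or state that the V3 form asks about both conditions, or drop the with-and-without contrast for this outcome. A V1 rating would be about 100 short forms if completed per patient, and fewer if per staff member; the plan does not say which.
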